a) Aim 2: Pilot testing with ~50 AGYW-FC dyads (~100 total participants) to establish acceptability and feasibility in preparation for the RCT in phase 2
Recruitment, enrolment and procedures for AIM 2

We will pilot test the revised IMARA curriculum with ~50 new AGYW-FC dyads, using the same eligibility and recruitment procedures described above. Groups will include approximately 6-8 dyads and participants will be followed for 12 months. The procedures for aim 2 are described next:

- We will schedule 8-10 dyads in each cohort to comprise one group. Upon arrival at the research site (Philippi village), trained staff will review consent and assent documents, ensuring comprehension and evaluating if participants are willing to participate.
- Following the consent/assent process, all AGYW and FC will complete a baseline assessment via computer-assisted self-interview (approx. 1 ½ hours) and indicate their desire to test for HIV and STIs and willingness to take PrEP. If willing to test for HIV and STIs, both AGYW and their FC will receive HIV/STI counselling and testing. AGYW and FC have the option to refuse testing and still remain in the study.
- Randomization (control vs. intervention): We will randomize participants to treatment arm upon completion of the baseline assessment so as not to lose families due to bias in advance. Approximately 25 dyads will be randomly assigned to the health promotion group and ~25 dyads to IMARA. Randomization will follow the fish-bowl method, where equal numbers of RED and WHITE cards will be placed in the fish bowl. AGYW will select a card. The two intervention groups will take place in different rooms. The control and IMARA curricula are matched for time and attention.
- The first group session (approx. 3 hours) will be delivered immediately following randomization. Participants will be at site for 6.5 hours for their first session activities, including the baseline assessment and intervention.
- Participants will return one week later for day 2 of the intervention.
- The total time of the intervention is approximately 12 hours.
- Participants who agreed to test for HIV will be given their results at the end of day 1. If HIV positive, referral for care in the regular public ART clinics will be provided. For those who agreed to test for STIs, results will be ready by session 2. If positive, the DTHF nurse will provide STI risk reduction counselling and treatment. We will request the partner be treated as well.

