- For participants who are HIV negative and opt to take PrEP in our baseline survey, we will provide a one month PrEP prescription with a referral to public, youth friendly clinics currently offering PrEP. We will draw blood for safety monitoring of creatinine in

IMARA-1 Study Protocol

Protocol Title: Multilevel Comprehensive HIV Prevention Package for South African Adolescent Girls and Young Women

Protocol PI: [name]

Version 5.0: 14 May 2020

Approved 10JUN2019

Amendment approved xx-xxx-xxxx

accordance with the national guidelines. We will additionally test blood draws for Hepatitis B, in line with national guidelines, among participants who opt to take PrEP at the 6- and 12-month follow-up points. Urine will be tested for pregnancy. Renal function (e.g., creatinine clearance, CrCl) will be tested and all results will be supervised by a medical member of our team. Participants will receive the results with referral documents for the next dose of PrEP.

- At each follow up data collection point and after the second session, we will re-invite individuals for HIV and STI testing. We will also re-invite participants to receive PrEP, unless they accepted PrEP from us at a previous data collection timepoint, were linked to care, and are receiving PrEP from a clinic. Should they be willing to test and to use PrEP, the same procedures as above will apply. At the end of their first month post PrEP initiation and referral, the team will follow up on PrEP and ART uptake at clinics including where they plan to seek PrEP or ART services. We will also ask about whether side effects participants are experiencing when they come for their second visit a week after the first session. We encourage all our participants to contact us should they experience any side effects once they have started using PrEP. During follow-up visits at 6- and 12- months, we will additionally use dried blood spots (DBS) to assess adherence to PrEP among those who have accepted PrEP.
- We will implement extensive retention and tracking procedures (see retention and tracking procedures section below).
- We will re-interview AGYW and FC 6- and 12-months after baseline for preliminary evidence of feasibility and acceptability, particularly with regard to the procedures for HTC, STI and PrEP uptake, and linkage to care for treatment.

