B) Predictors and Mediators. Individual-Level. (1) HIV/AIDS/STI Knowledge, Attitudes, Beliefs, and Skills. AGYW and mothers will complete the *HIV/AIDS Knowledge Survey*, a measure of transmission routes and prevention strategies²⁰⁹ and AGYW will complete the *HIV/AIDS and STI Attitudes and Beliefs Survey* measuring: (a) general attitudes; (b) norms regarding prevention; (c) prevention intentions; (d) attitudes toward preventive acts; and (e) prevention skills (see Mukoma et. al., 2009).²¹⁰ (2) Mental Health and Emotion Regulation. Caregivers will complete the *Child Behavior Checklist (CBCL)* and AGYW will complete the *Youth Self-Report (YSR < 18 years)* or *Adult Self-Report (ASR ≥ 18 years)*. All three are widely-used and validated measures in isiXhosa of young people's mental health problems and generate raw and T-scores for internalizing (e.g., sadness, anxiety) and externalizing (e.g., fighting, swearing) syndromes.²¹¹⁻²¹³ AGYW will complete the *UCLA PTSD Index* to assess exposure to trauma and violence,²¹⁴ and they will complete the 6-item *Structured Interview for Disorders of Extreme Stress* to report emotion regulation.²¹⁵ (3) PrEP and HTC knowledge, Attitudes, and Adherence. AGYW will indicate their knowledge and willingness to take PrEP using items from Hoff et al.,²¹⁶ and they will report on their attitudes toward HTC using Kalichman and Simbayi's²¹⁷ 5-item scale (both used and validated in South Africa). We will inquire about linkage to care (yes/no) for PrEP and HIV, and where appropriate we will assess adherence to PrEP and ART using the 3-item scale by Wilson et al.²¹⁸ Mothers will complete similar items about their attitudes toward HTC and PrEP for AGYW. Sociocultural-Level. Family context. AGYW will report on the strength of their attachment to mothers using the *Inventory of Parent and Peer Attachment*.^{219, 220} AGYW and mothers will indicate the level of parental monitoring, supervision and permissiveness using the *Parenting Style Questionnaire*²²¹ and on the quality and quantity of their HIV-risk related communication.^{222 71, 223} Structural-Level. (1) Gender dynamics. AGYW will report on their partners' age, perceptions of control over condom use, partners' resistance to condom use, and financial dependence on partners.⁹⁰ Items from the *Sexual Relationship Power Scale (SRPS)* will measure perception of relationship control and decision-making dominance.²²⁴ The *Power and Attitudes in Relationships (PAIR)* scale assesses gender roles and norms, perceived need to be in a relationship, women and men's division of household responsibility, and sexual assertion and power in decision-making.²²⁵ We will measure partner concurrency with items validated by Kalichman, Ntseane, Nthomang et al.²²⁶ and Harrison, Cleland, & Frohlich²²⁷ in SA. Gender-based violence will be assessed using items from the *WHO Multi-Country Study on Women's Health and Life Experiences*.²²⁸ We will examine partner sexual communication using items adapted from the *Sexual Risk Behavior Questionnaire*²²⁹ and Miller et al.²²² Items ask about a list of topics (e.g., using condoms), how often they were discussed, and whether the conversation was open and comfortable. (2) HIV/AIDS stigma. AGYW and mothers will complete the 9-item AIDS-Related Stigma Scale validated in isiXhosa and English. The scale is internally consistent and time stable.²³⁰ Participant Satisfaction. At the end of both workshop days, AGYW and mothers will complete an evaluation of the program.

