STI. At each assessment, we will collect urine to screen for *N. gonorrhoeae*, *C. trachomatis*, and *T. vaginalis*. We will give participants collection containers and escort them to a private, secure room in which to produce the specimen. Staff will decant the urine to centrifuge tubes labelled with unique, anonymous, subject-sample identifiers and store them in refrigerators. The BARC laboratory will use nucleic acid amplification technologies (NAAT) for STI testing^{234, 235} and email the results using a password protected server to us within one week. AGYW who test positive for an STI will be offered free single-session directly observed therapy by our Clinical nurse practitioner (CNP) and a medical officer on site with the following antimicrobials: *N. gonorrhoea* – Ceftriaxone 250 mg injection (Rocephin®); *C. trachomatis* – Azithromycin (Zithromax™); All HTC procedures will comply with the DTHF standard operating procedures.

Our staff and counsellors at our site are extensively trained and highly experienced conducting HTC with youth and adults. At baseline, HTC will be conducted following the workshop so as not to interfere with the day's activities. At follow-up, HTC will occur at the end of the assessments so as not to interfere with other survey materials. Urine samples will be sent to the BARC laboratory for testing and an HIV rapid test will be conducted. AGYW who test positive for HIV will be immediately linked to care at ART public clinics and an appointment for follow-up care will be arranged. The project coordinator working closely with the CNP nurse will track appointment attendance by reaching out to our referral clinics. An SOP is already in place where PrEP uptake data is obtained from these clinics and we will work with the existing

SOP to obtain our participants PrEP uptake information. For STI and HIV results, we will maintain subject-sample ID linkages in confidential logs kept in secure, locked storage. The DTHF has been using these procedures for many years with no adverse events. We will offer Pre-Exposure Prophylaxis (PrEP) to AGYW and FC at each assessment point. For interested participants, we will schedule an appointment at the DTHF clinic and assist with transportation or attendance, as needed, to the initial appointment

Data reduction, data analysis and expected outcomes

Expected outcomes

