AGYW will report on their risk behavior and provide biological specimens for STI and HIV testing. **(1) HIV/STI Risk Behaviors.** *AIDS-Risk Behavior Assessment (ARBA)*²³⁶ is a computer-assisted structured interview of self-reported sexual behavior, drug use, and HIV status derived from 5 well-established measures,²³⁷⁻²⁴² and used extensively in published research. The ARBA employs a skip structure so that questions initially answered “no” are not followed by more detailed questions. We will use specific indicators (e.g., number of partners), frequency measures, count variables (e.g., number of unprotected sex acts), and composite scores to assess risky sex. We will also calculate lifetime sexual behavior and the ratio of protected to unprotected sex acts. The measure has been used with SA adolescents. **(2) PrEP uptake.** **(3) HIV and STI incidence.**

Data Reduction and Analyses.

We will generate frequencies and summary statistics of predictor and outcome variables to screen and clean the data. We will check the success of randomization by comparing intervention groups on baseline variables using chi-square tests for categorical variables and t-tests or nonparametric Wilcoxon rank-sum tests for continuous variables. In subsequent analyses, we will control for predictor variables that are not balanced across arms at baseline. We also will check for differences between AGYW in IMARA-SA and FUEL-SA in subsequent analyses. We will create summary scores for AGYW on the following variables: (1) sexual activity, HIV and STI incidence, PrEP and HTC uptake; (2) individual drivers (mental health/emotion regulation; HIV/AIDS knowledge, attitudes, beliefs, skills; PrEP and HTC attitudes and beliefs); (3) sociocultural drivers (partner concurrency; family context); and (4) structural drivers (gender dynamics; HIV/AIDS stigma). We will conduct analyses on individual outcome indicators and on composite scores comprised of multiple indicators for the pilot study in aim 2.

Participant reimbursement

Participants will not be paid to participate in the intervention, but they will be reimbursed for their time and transport: AGYW and FC will each receive R120 for the theater test and R130 for the pilot test at each study visit.

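### PrEP uptake should be compared between arms with prespecified adjustment for the pre-randomisation PrEP opt-in answer, and the >50% PrEP milestone needs a defined time window

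*Combined protocol and SAP*

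**What the plan says.** In the Aim 2 recruitment and procedures text, AGYW and caregivers complete the baseline assessment and "indicate their desire to test for HIV and STIs and willingness to take PrEP". Allocation comes next: "We will randomize participants to treatment arm upon completion of the baseline assessment".

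The rule for the first prescription refers back to that survey: "For participants who are HIV negative and opt to take PrEP in our baseline survey", the study provides one month of PrEP and a clinic referral. There are later chances, after the second session and at each follow-up: "We will also re-invite participants to receive PrEP, unless they accepted PrEP from us at a previous data collection timepoint". The sentence then adds two further conditions: the participant must also have been linked to care and be receiving PrEP from a clinic. Someone who took the first prescription but is not in clinic care is therefore invited again.

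The same procedures give HIV results at the end of day 1. The specimen section places baseline HIV testing after the workshop and says that PrEP is offered at every assessment. On uptake after referral, it says that "PrEP uptake data is obtained from these clinics".

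The baseline questionnaire section, under Predictors and Mediators, states that "AGYW will indicate their knowledge and willingness to take PrEP". Data Reduction and Analyses says: "We will check the success of randomization by comparing intervention groups on baseline variables using chi-square tests" (for categorical variables), and then "we will control for predictor variables that are not balanced across arms at baseline". It gives no threshold for imbalance. PrEP uptake is a summary variable that is not split by time.

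The Protocol Summary and the specimen section set a milestone of more than 50% uptake of PrEP prescription, without a time window. The Aim 2 procedures make the move to phase 2 depend on the milestones.

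**The concern.** An answer recorded before allocation that triggers part of the outcome is likely to be one of its strongest baseline predictors. Letting a significance test decide whether to use it has two costs. When the arms look balanced, which is most of the time, the precision it could give is lost. When the arms differ by chance, but not enough to be flagged, the estimate is shifted and left uncorrected.

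The milestone is a separate matter and does not depend on the arm comparison. It feeds a go/no-go decision, and PrEP is re-offered several times. Without a window, the same data can pass or fail according to which prescriptions are counted.

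**Working it through.** **Inputs from the documents.** About 25 dyads per arm in the pilot; 525 dyads in the later RCT, so 525/2 ≈ 262 per arm; milestone >50%. The documents give no power calculation or rate for PrEP uptake, so there is no figure to reproduce.

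**Assumptions.** b = share of AGYW opting in at baseline = 50%. c = share of opt-ins prescribed at baseline, the same in both arms, varied from 40% to 100%. Later uptake p = 20% (FUEL) and 40% (IMARA) among everyone not prescribed at baseline. The plan's rule is read as: adjust if chi-square p < 0.05. Tests are two-sided at 0.05. Clustering by session group is ignored.

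**Chance imbalance, 25 per arm (exact binomial enumeration).** The smallest difference flagged near 50% is 16 vs 9, or 28 points (p = 0.048). The check fires in 6.5% of randomisations. A difference of at least 20 points arises in 20% and goes unflagged in 14%. The resulting shift in the unadjusted difference is imbalance × gap in uptake between opt-ins and others. For a 20-point imbalance this is 0.20 × 0.40 = 8 points to 0.20 × 0.80 = 16 points.

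**Precision.** Uptake among opt-ins is c + (1 − c)p; among the rest it is p. With c = 100%, overall uptake is 0.5 + 0.5 × 0.20 = 60% vs 0.5 + 0.5 × 0.40 = 70%, a difference of 10 points.
- Unadjusted variance: (0.60 × 0.40 + 0.70 × 0.30)/25 = 0.0180, SE 13.4 points.
- Stratified variance: opt-ins contribute 0; the others contribute 0.20 × 0.80 + 0.40 × 0.60 = 0.40. So 0.5 × 0.40/25 = 0.0080, SE 8.9 points.

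With c = 40%, opt-in uptake is 52% vs 64% and overall uptake is 36% vs 52%, a difference of 16 points.
- Unadjusted: (0.36 × 0.64 + 0.52 × 0.48)/25 = 0.0192, SE 13.9 points.
- Stratified: (0.5 × 0.48 + 0.5 × 0.40)/25 = 0.0176, SE 13.3 points.

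Stratifying does not change the risk difference being estimated.

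**Power by simulation** (at least 100,000 trials per scenario; stratified = Cochran-Mantel-Haenszel test by opt-in answer):

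| c | Pilot, 25 per arm: rule vs stratified | 262 per arm, if the same rule were used: rule vs stratified |
|---|---|---|
| 100% | 11% vs 18% | 69% vs 95% |
| 80% | 15% vs 18% | 81% vs 93% |
| 60% | 19% vs 19% | 90% vs 94% |
| 40% | 23% vs 22% | 96% vs 97% |

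The rule does not inflate type I error. At 262 per arm, with c = 100% and 30% later uptake in both arms, it was 3.4%, against 4.9% stratified.

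**Milestone.** With 30% later uptake among those not prescribed at baseline, cumulative uptake is bc + 0.30(1 − bc). For b = 40%, c = 100%: 40% from opt-ins alone; 0.40 + 0.30 × 0.60 = 58% cumulatively. For b = 40%, c = 80%: 32% against 0.32 + 0.30 × 0.68 = 52%.

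**The case against.** **The documents cover phase 1 only.** The design section says that the RCT will be a separate application, and no RCT analysis plan is included. A reader might infer from the 262-per-arm column that the RCT is underpowered as planned. The documents do not support that; the column shows only what would follow if the pilot's rule were carried forward.

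**The gain depends on c.** This stands. The 69% vs 95% contrast is the extreme case and shrinks to 96% vs 97% at c = 40%. If uptake means uptake at the clinics, the opt-in answer may predict it only moderately.

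**Stratifying is not free at pilot size.** This also stands: at c = 40% the pilot loses about a point of power (23% vs 22%).

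**Opt-in prescriptions are not fixed before allocation.** A reader might infer that the survey answer decides who is offered PrEP, so that these events are settled beforehand. The text says otherwise. PrEP is offered at every assessment, and HIV results follow the first session, so acceptance may depend on arm. The data-collection section also words referral differently (a negative HIV test and/or a wish for PrEP); this must be reconciled with the Aim 2 rule. The point survives because the proposed stratifier is the answer, which does precede allocation, and not the prescription. The gain does not require c to be equal: at 262 per arm, with 90% of IMARA and 80% of FUEL opt-ins prescribed, power is 95% (rule) vs 99% (stratified); reversed, it is 47% vs 66%.

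**The milestone wording naturally includes opt-in prescriptions.** That is the plainer reading, but it does not say whether prescriptions at later re-invitations count, or up to when.

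**Conclusion.** The point holds as one of efficiency and definition. Randomisation keeps the unadjusted comparison unbiased on average; a reader who infers a biased estimate goes further than the documents allow. What is lost is the use of a probably strong predictor and protection against unflagged chance imbalance.

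Under the stated assumptions, the pilot moves from 11% to 18% power at best and from 23% to 22% at worst, so it remains uninformative on the arm contrast. The main benefit of the adjustment is to establish a sound analysis before phase 2. The milestone gap has the more direct consequence, since 40% or 58% can come from the same data.

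The opt-in share, prescription share, later uptake and p < 0.05 trigger are all assumed. Similar treatment of HIV-testing uptake might seem to follow, but no calculation here supports it and none is proposed.

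**What to change.** 1. In Data Reduction and Analyses, for the between-arm comparison of PrEP uptake in AGYW, replace adjustment for unbalanced predictors with: *The comparison will be adjusted for, or stratified by, the baseline PrEP opt-in answer, whatever the observed balance.* Choose one form in advance; a Mantel-Haenszel risk difference with a Cochran-Mantel-Haenszel test would serve. Name the single survey item that triggers the prescription, because the plan does not say whether it is the same as the willingness items in the questionnaire.
2. Tabulate by arm the prescriptions that follow the baseline opt-in, separately from later uptake. Before looking at the data, state which of these, and over what time window, the >50% milestone uses.

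A table of uptake among AGYW who did not opt in is optional and descriptive only (about 12 per arm if half opt in).

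The cost is wording and one extra table. The answers are already collected, and no visit or procedure changes. The downside is a slight loss of pilot power if the answer turns out to be weakly related to uptake.

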
Survey questions added for 6 and 12-month surveys (see Appendix 1): We will ask a set of questions about the COVID-19 virus at 6 and 12 months. These measures will assess the extent to which the outbreak has impacted participants' lives and behaviors, including their sexual behavior, alcohol and drug use, and access to clinical care. Questions will also explore what participants have done to cope with COVID-19. Questionnaire items were adapted from the COVID-19 Exposure and Family Impact Survey,²³¹ the COVID-19 Questionnaire-Child Self-Report Primary version from the Environmental Influences on Child Health Outcomes (ECHO),²³² the CoRonaviruS Health Impact Survey (CRISIS),²³³ and the iTech/ATN survey.

Biological Specimen collection, handling and testing

Biological specimen collection. We have carefully considered availability of procedures for age-appropriate biologically verified HIV and STIs. We have sought out the latest available but least invasive methods based on preparatory research of available test kits, assays, lab space, and pricing. As such, we have chosen finger prick HIV tests and urine tests for STIs (chlamydia, gonorrhea, trichomonas). We will use trained and certified counsellors, clinic and lab teams to gather HIV/STI biological data and to conduct referrals for confirmatory testing and treatment. For participants interested in PrEP, our staff are also trained to draw blood, conduct creatinine assessments, and test for Hepatitis B and DBS samples for PrEP adherence. These specimens will be used to monitor STI incidence > 20% (with 100% receiving DOT), uptake of HTC > 70%, uptake of PrEP prescription > 50% and retention at 6 months of > 80%. While HIV tests will be done at site, urine and blood specimens will be sent to BARC for testing. We will offer AGYW PrEP at each assessment, unless the participant has accepted PrEP from us during a previous data collection timepoint, been linked to care, and is receiving PrEP from a clinic.

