3.2. Risk/Benefits to participants

Benefits/risks to participants: We anticipate that this study will provide immediate benefits to the participants through participating in sessions, testing for HIV/STIs and receiving treatment. Participants will also benefit by being offered PrEP hence preventing HIV infection.

Potential Risks.

This research includes a number of potential risks which we outline below. We detail procedures to minimize these risks.

- Biological specimen collection.** We have carefully considered availability of procedures for age-appropriate biologically verified HIV and STIs. We have sought out the latest available but least invasive methods based on preparatory research of available test kits, assays, lab space, and pricing. Our team is well trained to handle all testing procedures and complete referrals where necessary.
- Interested AGYW and FC will provide urine for STI testing, saliva/finger prick for HIV testing, and blood draws for PrEP at all three time points. AGYW and FC who take up PrEP will also be invited to provide a dried blood spot to test for adherence to PrEP at

follow-up visits. Consistent with our previous studies, we will provide participants with urine collection containers and escort them to a private, secure room in which to produce the specimen. We will train staff to use proper procedures to obtain urine from subjects and approved procedures for the safe handling of urine. Staff will decant the urine to centrifuge tubes labeled with unique, anonymous, subject-sample identifiers and store the specimens in refrigerators. We will send our samples to BARC laboratory will use nucleic acid amplification technologies (NAAT) for STI testing and email the results using a password protected server to study staff in the US within one week. AGYW and FC who test positive for an STI will be referred to our DTHF Medical Officers for treatment. We will adhere to all DTHF standard operating procedures for management of STIs and will at minimum include a free single-session directly observed therapy with the following antimicrobials, each of which constitutes a single session therapeutic regimen: N. gonorrhoea – Ceftriaxone 250 mg injection (Rocephin®) AND Azithromycin (Zithromax™) 1g orally; C. trachomatis – Azithromycin (Zithromax™) 1g orally; T. vaginalis – Metronidazole (Flagyl™) 2g orally HIV testing and counseling (HTC) will be conducted by DTHF trained and certified staff at the clinical research sites

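### Hepatitis B testing is written only for the 6- and 12-month visits: no test is written at a baseline PrEP start, and cover for earlier starters is ambiguous

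*Combined protocol and SAP*

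**What the plan says.** The PrEP bullet in the procedures for Aim 2 (section 2) begins with the baseline offer: "For participants who are HIV negative and opt to take PrEP in our baseline survey, we will provide a one month PrEP prescription". Two safety tests carry no visit limit: "We will draw blood for safety monitoring of creatinine" and "Urine will be tested for pregnancy". Hepatitis B is brought in as an additional test and is the only one tied to visits: "Hepatitis B, in line with national guidelines, among participants who opt to take PrEP at the 6- and 12-month follow-up points". A medical member of the team oversees the results, which the participant receives with her referral papers for further PrEP.

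The next bullet offers PrEP again at later contacts, "unless they accepted PrEP from us at a previous data collection timepoint, were linked to care, and are receiving PrEP from a clinic".

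Two other places bear on the question. Biological Specimen collection, handling and testing says: "For participants interested in PrEP, our staff are also trained to draw blood, conduct creatinine assessments, and test for Hepatitis B". It names no visit. Section 3.2 lists "blood draws for PrEP at all three time points". It names no assay.

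On HIV status, the Treatment regimen row of the Protocol Summary and the PrEP bullet both confine PrEP to HIV-negative participants. The Formulation paragraph under Procedures for PrEP supplies willing young women straight away and sets no HIV condition. Data Collection Procedures joins a negative test and a wish for PrEP by and/or when it describes referral to the medical officer. Testing itself is optional: "AGYW and FC have the option to refuse testing and still remain in the study".

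**The concern.** The same tablet is started under different written safety cover depending on the visit. A participant who starts at 6 or 12 months has a hepatitis B test written for that visit. One who starts at baseline, when PrEP is first offered, does not. The protocol treats hepatitis B as part of PrEP safety testing and cites national guidelines for it, as it does for creatinine, and gives no reason why the test should depend on the visit. A baseline starter's referral papers would therefore carry no hepatitis B result that the protocol requires.

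A smaller concern is that the condition for supply is not stated the same way throughout. A willing participant who declines the HIV test fits the Formulation paragraph but not the PrEP bullet or the summary.

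At stake are participant safety procedures in a pilot that enrols minors and rehearses the procedures of the phase 2 trial. Nothing here touches the analysis.

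**Working it through.** There is no figure in the plan to reproduce, so the check sets the relevant places side by side.

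**Step 1: is a baseline hepatitis B test written anywhere?** The places that deal with PrEP start or PrEP blood are the summary, the Aim 2 procedures, Procedures for PrEP, Data Collection Procedures, Biological Specimen collection, and section 3.2. The only sentence that schedules hepatitis B is the one in the PrEP bullet, and it names 6 and 12 months. Biological Specimen collection describes what staff are trained to do. Section 3.2 shows that PrEP blood is drawn at baseline, but not that it is tested for hepatitis B. Of the three tests in the bullet, one (hepatitis B) is limited by visit and two (creatinine, pregnancy) are not.

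**Step 2: what does the hepatitis B sentence require?** The time phrase can attach to the testing (broader reading) or to the choice of PrEP (narrower reading). The parallel with the bullet's opening, which speaks of opting at baseline, favours the narrower reading but does not prove it.

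| PrEP started at | First written test, broader reading | First written test, narrower reading |
|---|---|---|
| Baseline | 6 months | None, unless she opts again at 6 or 12 months |
| 6 months | 6 months | 6 months |
| 12 months | 12 months | 12 months |

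A start after the second session, about one week in, is not named either and falls in the first row for practical purposes.

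**Step 3: timing on the broader reading.** Start to first written test: 6 months. Study supply: 1 month. Interval after the supply ends: 6 − 1 = 5 months.

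**Step 4: who is left out on the narrower reading.** Re-invitation is withheld only if three things hold together: the participant took PrEP from the study before, was linked to care, and is now supplied by a clinic. She is not asked to opt again, so no study test is written for her. Other earlier starters are re-invited and would be tested if they opt again.

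**Step 5: how many.** The number of baseline starters is not given. The possible range is 0 to about 50 AGYW, or 0 to about 100 if caregivers are counted, less any who are HIV positive. That range covers everyone and says nothing about the likely number.

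**Step 6: HIV condition.** The summary and the PrEP bullet require HIV-negative status. The re-invitation bullet ties PrEP to willingness to test as well as to use it. The Formulation paragraph asks for willingness alone. The and/or in Data Collection Procedures governs referral to a clinician, not dispensing. The section on PrEP initiation has a medical officer or nurse practitioner start the drug.

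**The case against.** The strongest reply is about timing. Version 5.0, dated 14 May 2020, reads as a mid-study amendment. Section 3.1 has a month-six consent addendum for changes since launch, the COVID-19 questions were not in the baseline survey, and the hepatitis B sentence names only the follow-up visits. Adding a test for the visits that remain is ordinary practice. The timeline table has blank cells in the text available, so whether baseline was still open cannot be shown. This largely stands: the baseline half of the point may be moot, and the catch-up test may be all that matters.

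Second, the broader reading already supplies a catch-up test at 6 and 12 months. That is true, but the sentence does not settle which reading is meant.

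Third, the group left out on the narrower reading is by definition supplied by a clinic, and staff can monitor participants referred there. This lowers the practical risk. It does not put a hepatitis B result on the study file.

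Fourth, blood goes to an outside laboratory while supply is immediate, so a result for a 6- or 12-month starter would normally also follow her first supply. This stands too: the contrast is between having a test written at the start and not having one, rather than between a result in hand and none.

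Fifth, national guidelines or site procedures may require a baseline test. They are not in the documents, so this can be neither confirmed nor ruled out.

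A reader might infer that baseline starters go untested throughout, or that the plan hands PrEP to people who are HIV positive or untested. The documents support neither. The broader reading tests baseline starters at 6 months, section 3.2 leaves room for a baseline test, two places set the HIV-negative condition, and a clinician starts PrEP.

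**Conclusion.** The point holds as a gap and an ambiguity in the written procedure. On either reading, no hepatitis B test is written at a baseline PrEP start. On the broader reading the first written test comes about 6 months after that start, 5 months after the study supply ends. On the narrower reading, earlier starters now supplied by a clinic have no study test. This rests on the text alone and assumes that no outside guideline or site procedure fills the gap. If baseline was complete when Version 5.0 took effect, only the catch-up part remains live.

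The inconsistent HIV condition is real but minor: unclear wording, tempered by clinician initiation.

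A reader might put a number on the first point by applying the pilot's target of more than 50% PrEP uptake to baseline. The documents do not support that, because the milestone does not say that uptake occurs at baseline. Nor do they describe a clinical harm or say when a hepatitis B result must be known, so none is asserted. The change is worth making because it is protective and cheap. No effect on an endpoint or milestone is claimed.

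**What to change.** Replace the hepatitis B sentence in the PrEP bullet of the Aim 2 procedures with:

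> We will test for hepatitis B, in line with national guidelines, at whichever visit a participant (AGYW or FC) starts PrEP with us, on the blood drawn for creatinine; anyone who started earlier and has no hepatitis B result on file will be tested at her next in-person visit, whether or not she is re-invited to PrEP.

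If baseline is already complete, only the second clause applies. The wording also covers a start after the second session. It does not decide whether supply waits for laboratory results.

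Two minor companion edits:

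- In the Formulation paragraph, state that the one-month supply goes to willing participants with a negative HIV test at that visit, to match the summary and the PrEP bullet.
- In Data Collection Procedures, keep referral to the medical officer open to anyone who wants PrEP, and add that supply requires a negative HIV test. Simply changing and/or to and would be a mistake: it could cut off an untested participant from the clinician who could offer the test.

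The cost is these wording changes and one hepatitis B assay per early starter. If the broader reading was intended all along, the catch-up assay is not an added cost. At a PrEP start the test uses blood already drawn for creatinine. At follow-up it means a blood draw for those not otherwise having one. Participants surveyed by telephone can be tested at the on-site clinical assessment already foreseen in section 3.1.
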